#### **10.8.8.5.6. Unscheduled Visit for a Grade 3 or Suspected Grade 4 Reaction**

If a Grade 3 local reaction ([Section 8.3.4.2](#)), systemic event ([Section 8.3.4.3](#)), or fever ([Section 8.3.4.4](#)) is reported in the e-diary, a telephone contact should occur to ascertain further details and determine whether a site visit is clinically indicated. If a suspected Grade 4 local reaction ([Section 8.3.4.2](#)), systemic event ([Section 8.3.4.3](#)), or fever ([Section 8.3.4.4](#)) is reported in the reactogenicity e-diary, a telephone contact or site visit should occur to confirm whether the event meets the criteria for Grade 4.

A site visit must be scheduled as soon as possible to assess the participant unless any of the following is true:

- The participant is unable to attend the unscheduled visit.
- The local reaction/systemic event is no longer present at the time of the telephone contact.
- The participant or his/her parent(s)/legal guardian recorded an incorrect value in the reactogenicity e-diary (confirmation of a reactogenicity e-diary data entry error).
- The PI or authorized designee determined it was not needed.
- The investigator or authorized designee confirmed severe reactogenicity assessment via medical records and/or telehealth assessment.

This telephone contact will be recorded in the participant's source documentation and the CRF.

If the participant is unable to attend the unscheduled visit, or the PI or authorized designee determined that it was not needed, any ongoing local reactions/systemic events must be assessed at the next study visit.

#### **10.8.8.5.7. COVID-19 and MIS-C Surveillance**

If a participant experiences any of the following (irrespective of perceived etiology or clinical significance), the participant or his/her parent(s)/legal guardian is instructed to contact the site immediately. If confirmed to be a potential COVID-19 illness, the site should schedule and conduct either an in-person or telehealth visit as soon as possible, optimally within 3 days after symptom onset (and at the latest 4 days after symptom resolution). Refer to [Section 10.8.8.2.1](#) for more details on COVID-19 and MIS-C surveillance.

- A diagnosis of COVID-19;
- Fever;
- New or increased cough;

- New or increased shortness of breath;
- Chills;
- New or increased muscle pain;
- New loss of taste/smell;
- Sore throat;
- Diarrhea;
- Vomiting.

Note that:

- The CDC list of COVID-19 symptoms can be found at: <https://www.cdc.gov/coronavirus/2019-ncov/symptoms-testing/symptoms.html>. The additional symptoms listed by the CDC (ie, those not listed in the above protocol-defined list) should not trigger a potential COVID-19 illness visit unless, in the opinion of the PI, deemed necessary.
- If new symptoms are reported within 4 days after resolution of all previous symptoms, they will be considered to be part of a single illness and a second illness visit is not required.
- Surveillance of potential COVID-19 symptoms should continue even if a participant has a positive SARS-CoV-2 test earlier in the study.

During the 7 days following the vaccination, potential COVID-19/MIS-C symptoms that overlap with specific systemic events (ie, fever, chills, new or increased muscle pain, diarrhea, vomiting) should not trigger a potential COVID-19 illness visit unless, in the investigator's opinion, the clinical picture is more indicative of a possible COVID-19 illness than vaccine reactogenicity. If, in the investigator's opinion, the symptoms are considered more likely to be vaccine reactogenicity, but a participant is required to demonstrate that he or she is SARS-CoV-2–negative, a local SARS-CoV-2 test may be performed. If the test result is positive, the symptoms should be recorded as a potential COVID-19 illness; if not, the symptoms that overlap with systemic events should be recorded in the reactogenicity e-diary or as AEs, if not captured in the reactogenicity e-diary.

The participant or his/her parent(s)/legal guardian is also instructed to contact the site immediately should the participant receive a positive SARS-CoV-2 test (NAAT or rapid antigen) result that is not accompanied by any symptoms. A potential COVID-19 visit is **not** required in this instance, but details of the positive test should be recorded in the designated CRF.

The participant or his/her parent(s)/legal guardian may utilize a COVID-19 illness e-diary through an application (see [Section 8.3.4](#)) installed on a provisioned device or on the participant's or his/her parent(s)/legal guardian's own personal device to prompt him/her to report a diagnosis of COVID-19 or any symptoms of COVID-19. Note that this does not substitute for a participant's routine medical care. Therefore, the participant or his/her parent(s)/legal guardian should be encouraged to seek care, if appropriate, from the participant's usual provider.

#### **10.8.8.5.8. Potential COVID-19 Illness Visit (Optimally Within 3 Days After Potential COVID-19 Illness Onset)**

This visit may be conducted as an in-person or telehealth visit; a telehealth visit involves the sharing of healthcare information and services via telecommunication technologies (eg, audio, video, videoconferencing software) remotely, thus allowing the participant and investigator to communicate on aspects of clinical care.

As a participant's COVID-19 illness may evolve over time, several contacts may be required to obtain the following information:

- Record details of any of the prohibited medications specified in [Section 10.8.6.9.1](#) received by the participant if required for his or her clinical care.
- Record nonstudy vaccinations as described in [Section 10.8.6.9](#).
- Record AEs as described in [Section 8.4](#). Note: Potential COVID-19/MIS-C illnesses with their sequelae should not be recorded as AEs, with the exception of those assessed by the investigator as related to study intervention or those meeting the criteria for SAEs.
- If the visit is conducted in person, obtain a nasal (midturbinate) swab (collected by site staff). Alternatively, if conducted by telehealth, instruct the participant or his/her parent(s)/legal guardian to self-collect a nasal (midturbinate) swab at home and ship it for assessment at the central laboratory.
- Collect COVID-19–related standard-of-care clinical and laboratory information. This includes, but is not limited to:
  - Symptoms and signs, including
    - Clinical signs at rest indicative of severe systemic illness (RR  $\geq$ 30 breaths per minute, HR  $\geq$ 125 beats per minute, SpO2  $\leq$ 93% on room air at sea level, or PaO2/FiO2  $<$ 300 mm Hg).
    - Evidence of shock (SBP  $<$ 90 mm Hg, DBP  $<$ 60 mm Hg, or requiring vasopressors).
    - Significant acute renal, hepatic, or neurologic dysfunction.

- Respiratory failure (defined as needing high-flow oxygen, noninvasive ventilation, mechanical ventilation, or ECMO).
- Clinical diagnosis.
- Local laboratory SARS-CoV-2 test result(s). Note that if it is routine practice to perform a repeat local SARS-CoV-2 test for any reason, then a repeat nasal (midturbinate) swab should also be obtained and shipped for assessment at the central laboratory.
- Full blood count.
- Blood chemistry, specifically creatinine, urea, LFTs, and CRP.
- Imaging results (eg, computed tomography or MRI scan) to document neurologic dysfunction.
- Number and type of any healthcare contact; duration of hospitalization and ICU stay.
- Death.
- Complete the source documents.
- The investigator or an authorized designee completes the CRFs.

#### **10.8.8.5.9. SARS-CoV-2 NAAT Results**

Nasal (midturbinate) swabs for SARS-CoV-2 NAAT are obtained at:

- Visit B1: Contributes to the determination of a participant's baseline SARS-CoV-2 infection status.
- Potential COVID-19 illness visits: To determine whether symptoms experienced by the participant fulfill the COVID-19 case definition.

Research laboratory-generated positive results from the vaccination visit swabs, and all results from the illness visit swabs, will be provided to the site at the end of the study and, therefore, cannot be relied upon to direct clinical care. The participant or his/her parent(s)/legal guardian should be directed to seek additional testing through the participant's primary healthcare provider at a licensed clinical laboratory when the participant is exhibiting potential COVID-19 symptoms or otherwise receiving a positive result and counseled on whether to take any precautionary measures pending confirmatory testing, as per local guidance.

#### **10.8.8.5.10. Additional Procedures for Monitoring of Potential Myocarditis or Pericarditis**

Any study participant who reports the following within 6 weeks after the study vaccination:

- Acute chest pain, or
- Shortness of breath, or
- Palpitations, or
- Any other symptom(s) that might be indicative of myocarditis or pericarditis, **must be evaluated by a cardiologist** for possible myocarditis or pericarditis.

In addition to a clinical evaluation, the following should be performed:

- ECG and
- Measurement of the troponin level

If myocarditis or pericarditis is suspected based upon the initial evaluation, the following should also be performed:

- Cardiac echocardiogram and/or
- Cardiac magnetic resonance study

Details of the symptoms reported, and results of the investigations performed, will be recorded in the CRF.

Any diagnosis of myocarditis or pericarditis is considered an important medical event and must be reported as an SAE (refer to [Section 8.4.1.1](#) and [Section 8.4.3](#)). Other diagnoses should be recorded as AEs or SAEs, as appropriate. Refer also to [Section 10.8.8.4.1](#).

#### **10.8.8.5.11. Additional Procedures for Monitoring of Potential Menstrual Cycle Disturbances**

Any female study participant who reports any symptoms that may indicate a disturbance of their normal menstrual cycle (including, but not exclusively, heavy menstrual bleeding, amenorrhea, irregular periods) following receipt of study intervention until 6 months after the last vaccination should be specifically evaluated by the investigator. Details of the symptoms, menstrual history, and results of any investigations performed will be recorded in the designated CRF.

#### **10.8.8.5.12. Communication and Use of Technology**

In a study of this nature that requires events to be reported outside of scheduled study visits, it is vital that communication between the study site and the participant is maintained to ensure that endpoint events are not missed. This study will employ various methods, tailored to the individual participant, to ensure that communication is maintained and study information can be transmitted securely. Using appropriate technology, such as a study application, a communication pathway between the participant, as appropriate, and the study site staff will be established. The participant or the participant's parent(s)/legal guardian, as appropriate, may be able to utilize his or her own devices to access this technology, or use a device provided by the sponsor. Traditional methods of telephone communication will also be available. The technology solution may facilitate the following:

- A platform for recording local reactions and systemic events (reactogenicity e-diary) – see [Section 8.3.4](#).
- Contact with the investigator, including the ability of the participant or his/her parent(s)/legal guardian to report whether or not the participant has experienced symptoms that could represent a potential COVID-19 illness (COVID-19 illness e-diary) – see [Section 10.8.8.5.7](#).
- If a participant or his/her parent(s)/legal guardian is not actively completing the COVID-19 illness e-diary, the investigator or designee is required to contact the participant or his/her parent(s)/legal guardian to ascertain why and also to obtain details of any missed events.
- Messages of thanks and encouragement from the study team.

#### **10.8.9. Statistical Considerations for Substudy B**

See [Section 9](#) for general protocol statistical considerations and see specific Substudy B statistical considerations below.

##### **10.8.9.1. Statistical Hypotheses**

The immunogenicity primary objective is to assess the noninferiority with respect to level of neutralizing titer and seroresponse rate of the anti-XBB.1.5 immune response induced by BNT162b2 (Omi XBB.1.5) 30 µg given as a single dose to COVID-19 vaccine-naïve participants who were previously exposed to SARS-CoV-2 relative to the immune response elicited by BNT162b2 (Omi XBB.1.5) 30 µg given to vaccine-experienced participants in Substudy A. The primary objective will be evaluated by the following 2 hypotheses:

- The first null hypothesis ( $H_0$ ) is

$$H_0: \ln(\mu_1) - \ln(\mu_2) \leq \ln(0.67) \text{ vs } H_1: \ln(\mu_1) - \ln(\mu_2) > \ln(0.67)$$

where  $\ln(0.67)$  corresponds to a 1.5-fold margin for noninferiority and

- $\ln(\mu_1)$  is the natural log of the geometric mean of SARS-CoV-2 Omi XBB.1.5–neutralizing titers measured at 1 month after BNT162b2 (Omi XBB.1.5) 30 µg given as a single dose to COVID-19 vaccine-naïve participants who were previously exposed to SARS-CoV-2;
- $\ln(\mu_2)$  is the natural log of the geometric mean of SARS-CoV-2 Omi XBB.1.5–neutralizing titers measured at 1 month after BNT162b2 (Omi XBB.1.5) 30 µg given to vaccine-experienced participants in Substudy A.

- The second null hypothesis ( $H_0$ ) is

$$H_0: p_1 - p_2 \leq -0.1 \text{ vs } H_1: p_1 - p_2 > -0.1$$

where -10% is the noninferiority margin for seroresponse and

- $p_1$  is the percentage of participants with seroresponse to the Omi XBB.1.5 strain at 1 month after BNT162b2 (Omi XBB.1.5) 30 µg given as a single dose to COVID-19 vaccine-naïve participants who were previously exposed to SARS-CoV-2;
- $p_2$  is the percentage of participants with seroresponse to the Omi XBB.1.5 strain at 1 month after BNT162b2 (Omi XBB.1.5) 30 µg given to vaccine-experienced participants in Substudy A.

Seroresponse is defined as achieving a  $\geq 4$ -fold rise from baseline (before the study vaccination). If the baseline measurement is below the LLOQ, the postvaccination measure of  $\geq 4 \times \text{LLOQ}$  is considered seroresponse.

Noninferiority based on GMR will be declared if the lower limit of the 2-sided 95% CI for the GMR is greater than 0.67; noninferiority based on seroresponse will be declared if the lower limit of the 2-sided 95% CI for the difference in percentages of participants with seroresponse is greater than -10%.

#### 10.8.9.1.1. Estimands

The estimands corresponding to the primary objectives are described in the table in [Section 10.8.3](#).

The safety primary objective evaluations are based on the safety population. In general, completely missing reactogenicity data (ie, all 7 days of collection were missing) will not be imputed. For partially missing reactogenicity data (eg, 1-6 days of reactogenicity data are available), it is assumed that no reactions or events were experienced on the missing days. Missing AE start dates will be imputed according to Pfizer safety rules. No other missing information will be imputed in the safety analysis.

The estimands to evaluate the immunogenicity objectives are based on the evaluable immunogenicity population (Section 10.8.9.2). These estimands estimate the vaccine effect in the hypothetical setting where participants follow the study schedules and protocol requirements as directed. Missing antibody results will not be imputed. Immunogenicity results that are below the LLOQ will be set to  $0.5 \times \text{LLOQ}$  in the analysis. This may be adjusted once additional data on the assay characteristics become available.

#### 10.8.9.1.2. Multiplicity Adjustment

The 2 hypotheses for the primary objective will be evaluated sequentially using a 1-sided alpha of 0.025. Noninferiority based on GMR will be evaluated first, followed by seroresponse rate difference.

#### 10.8.9.2. Analysis Sets

For the purpose of analysis, in addition to the analysis sets defined in [Section 9.2](#), the following analysis sets are defined for this substudy:

Population	Description
Evaluable immunogenicity	All eligible assigned participants who receive the study intervention to which they are assigned, have at least 1 valid and determinate immunogenicity result from the blood sample collected within an appropriate window, and have no other important protocol deviations as determined by the clinician.
All-available immunogenicity	All assigned participants who receive the study intervention and have 1 valid and determinate immunogenicity result after vaccination.

#### 10.8.9.3. Statistical Analyses

The SAP will be developed and finalized before any analyses are performed and will describe the analyses and procedures for accounting for missing, unused, and spurious data. This section is a summary of the planned statistical analyses of the substudy endpoints.

##### 10.8.9.3.1. General Considerations

Refer to [Section 9.3.1](#) for general considerations of statistical analyses.

### 10.8.9.3.2. Primary Endpoint(s)/Estimand(s) Analysis

Endpoint	Statistical Analysis Methods
Safety	
Descriptive statistics will be provided for each reactogenicity endpoint by age subgroup (12-17 years, 18-55 years, >55 years) and overall. Local reactions and systemic events from Day 1 through Day 7 after each vaccination (where Day 1 is the day of vaccination) will be presented by severity and cumulatively across severity levels. Descriptive summary statistics will include counts and percentages of participants with the indicated endpoint and the associated Clopper-Pearson 95% CIs.
 
AEs and SAEs will be categorized according to MedDRA terms. Counts, percentages, and associated Clopper-Pearson 95% CIs of AEs from the study vaccination through 1 month and SAEs from the study vaccination through 6 months after the study vaccination will be provided by age subgroup and overall.

Immunogenicity	
 
• GMR of SARS-CoV-2 Omi XBB.1.5–neutralizing titers at 1 month after the study vaccination and the associated 2-sided 95% CIs will be calculated using the method described in Section 9.3.1.2. As the primary approach to calculate the GMR and CI for neutralizing titer, a linear regression model that includes terms for baseline neutralizing titer, age, and comparison group will be used to calculate the GMR and 95% CI, along with the model-based LS GMTs and associated 2-sided 95% CIs for each group.
 
• The percentages of participants with seroresponse to the SARS-CoV-2 Omi XBB.1.5 strain at 1 month after the study vaccination will be provided for each group. The difference in percentages of participants with seroresponse and the associated 2-sided 95% CIs will be calculated using the Miettinen and Nurminen method (see Section 9.3.1.1). The primary approach to calculate the difference in seroresponse rate between 2 comparison groups and the associated 95% CI will be the Miettinen and Nurminen method stratified by baseline neutralizing titer category (< median, ≥ median) and age group (< median, ≥ median).
 
• Noninferiority based on GMR will be established if the model-based lower bound of the 2-sided 95% CI for the GMR is greater than 0.67. Noninferiority based on seroresponse rate difference will be established if the lower bound of the 2-sided 95% CI for the difference in percentage is greater than 10%.
 

090177e1a159bed3\Approved\Approved On: 07-Aug-2024 18:34 (GMT)

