#### 10.8.9.5. Sample Size Determination

This substudy will enroll approximately 300 COVID-19 vaccine–naïve participants. The same number of vaccine-experienced participants will be selected from Substudy A as a control group to evaluate the immunogenicity primary objective. Assuming a 20% nonevaluable rate, approximately 240 evaluable participants in each group will contribute to the evaluation of the immunogenicity primary objective.

For comparisons based on GMR, common assay standard deviations at 1 month after the vaccination in log scale is assumed to be 1.35 based on data observed in Study C4591044. Table 11 provides the power to declare noninferiority under different assumptions of true GMRs of SARS-CoV-2 Omi XBB.1.5–neutralizing titers 1 month after BNT162b2 (Omi XBB.1.5) 30 µg given as a single dose to COVID-19 vaccine–naïve participants in Substudy B to 1 month after BNT162b2 (Omi XBB.1.5) 30 µg given to vaccine-experienced participants in Substudy A, using 1.5-fold margin. If the true GMR is 1.0, the study will have 90.0% power to declare noninferiority. If the true GMR is 0.9, there is 66.6% power to declare noninferiority.

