5.1. Hypotheses and Decision Rules

5.1.1. Immunogenicity Hypotheses

Substudy A

There is no formal hypothesis testing. All statistical analyses will be descriptive.

Substudy B

The immunogenicity primary objective is to assess the noninferiority with respect to level of neutralizing titer and seroresponse rate of the anti-XBB.1.5 immune response induced by BNT162b2 (Omi XBB.1.5) 30 µg given as a single dose to COVID-19 vaccine-naïve participants who were previously exposed to SARS-CoV-2 relative to the immune response elicited by BNT162b2 (Omi XBB.1.5) 30 µg given to vaccine-experienced participants in Substudy A. The primary objective will be evaluated by the following 2 hypotheses:

- The first null hypothesis (H_0) is

$$H_0: \ln(\mu_1) - \ln(\mu_2) \leq \ln(0.67) \text{ vs } H_1: \ln(\mu_1) - \ln(\mu_2) > \ln(0.67)$$

where $\ln(0.67)$ corresponds to a 1.5-fold margin for noninferiority and

- $\ln(\mu_1)$ is the natural log of the geometric mean of SARS-CoV-2 Omi XBB.1.5–neutralizing titers measured at 1 month after BNT162b2 (Omi XBB.1.5) 30 µg given as a single dose to COVID-19 vaccine-naïve participants who were previously exposed to SARS-CoV-2;
- $\ln(\mu_2)$ is the natural log of the geometric mean of SARS-CoV-2 Omi XBB.1.5–neutralizing titers measured at 1 month after BNT162b2 (Omi XBB.1.5) 30 µg given to vaccine-experienced participants in Substudy A.

- The second null hypothesis (H_0) is

$$H_0: p_1 - p_2 \leq -0.1 \text{ vs } H_1: p_1 - p_2 > -0.1$$

where -10% is the noninferiority margin for seroresponse and

- p_1 is the percentage of participants with seroresponse to the Omi XBB.1.5 strain at 1 month after BNT162b2 (Omi XBB.1.5) 30 µg given as a single dose to COVID-19 vaccine-naïve participants who were previously exposed to SARS-CoV-2;
- p_2 is the percentage of participants with seroresponse to the Omi XBB.1.5 strain at 1 month after BNT162b2 (Omi XBB.1.5) 30 µg given to vaccine-experienced participants in Substudy A.

Seroresponse is defined as achieving a ≥ 4 -fold rise from baseline (before the study vaccination). If the baseline measurement is below the LLOQ, the postvaccination measure of $\geq 4 \times \text{LLOQ}$ is considered seroresponse.

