Noninferiority based on GMR will be declared if the lower limit of the 2-sided 95% CI for the GMR is greater than 0.67; noninferiority based on seroresponse will be declared if the lower limit of the 2-sided 95% CI for the difference in percentages of participants with seroresponse is $> -10\%$.

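### The Substudy B primary-analysis table sets the seroresponse noninferiority threshold at +10% where the hypotheses, the SAP and the power table all use -10%

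*Protocol*

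**What the plan says.** Substudy B is the only substudy with formal hypotheses; Substudies A and C are descriptive. It has two primary immunogenicity hypotheses, one on the GMR and one on the difference in seroresponse rate, p1 - p2, where p1 is the vaccine-naïve group (Substudy B) and p2 the vaccine-experienced control group (Substudy A). Protocol Section 10.8.9.1.2 states the error control: "The 2 hypotheses for the primary objective will be evaluated sequentially using a 1-sided alpha of 0.025". The GMR comes first.

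The seroresponse criterion appears in three places:

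- **Protocol Section 10.8.9.1 (hypotheses).** H0 is p1 - p2 ≤ -0.1, and noninferiority is declared if the "lower limit of the 2-sided 95% CI for the difference in percentages of participants with seroresponse is greater than -10" percent.
- **SAP for Substudies A and B, Section 5.1.1.** It gives the same null hypothesis, "where -10% is the noninferiority margin for seroresponse and" the definitions of p1 and p2, and then the same -10% rule on the lower limit.
- **Protocol Section 10.8.9.3.2 (primary-analysis table).** Noninferiority is established if the "lower bound of the 2-sided 95% CI for the difference in percentage is greater than 10" percent, with no minus sign.

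The sample size section (10.8.9.5) uses a 10% margin and "approximately 240 evaluable participants in each group will contribute to the evaluation of the immunogenicity primary objective". Table 12 gives the resulting power.

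**The concern.** Section 10.8.9.3.2 is where a reader looks for the rule that decides the primary analysis, and it states an inequality on a confidence bound, not just the size of a margin. The same bullet prints the GMR threshold of 0.67 as it is to be applied, so the seroresponse figure would naturally be taken literally too. Read that way, the vaccine-naïve group must be shown to be more than 10 points better than the control group. Two groups with the same seroresponse rate would then almost never be called noninferior, and the power in Table 12 would not describe the test.

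The point also bears on a result already reported. Protocol Section 2.2.1 says Substudy B demonstrated noninferiority but does not state the threshold. Someone checking that statement against the primary-analysis table would apply the wrong criterion.

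**Working it through.** **Inputs**

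- Evaluable participants: n = 240 per group (Section 10.8.9.5), from 300 enrolled with 20% nonevaluable: 300 × 0.80 = 240. The control group is the same size.
- 1-sided alpha 0.025, i.e. the lower limit of a 2-sided 95% CI, z = 1.96 (Section 10.8.9.1.2).
- Assumed seroresponse rates: the six pairs in Table 12.
- Interval method: Miettinen and Nurminen. The plan stratifies it; the check is unstratified, because Table 12 gives no stratum assumptions.

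**Formula**

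For a threshold d on p1 - p2, the score-type (Farrington-Manning) approximation is

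power = Φ{[(p1 - p2) - d - 1.96 × SE0] / SE1}

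SE1 uses the assumed rates. SE0 uses the rates fitted under the restriction p1 - p2 = d.

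**Step 1: reproduce the plan's figure at 80% versus 80%, d = -0.10**

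- SE1 = √(2 × 0.80 × 0.20 / 240) = 0.03651.
- The restricted rates are 0.7411 and 0.8411, so SE0 = √[(0.7411 × 0.2589 + 0.8411 × 0.1589) / 240] = 0.03683.
- z = (0 + 0.10 - 1.96 × 0.03683) / 0.03651 = 0.762, so power = 77.7%. Table 12 says 77.7%.

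**Step 2: the same case with d = +0.10**

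- By symmetry SE0 is again 0.03683.
- z = (0 - 0.10 - 1.96 × 0.03683) / 0.03651 = -4.716, so power is about 0.0001%.

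**Step 3: every row of Table 12**

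| Control / Substudy B rate | Table 12 power | Recomputed, d = -10% | Recomputed, d = +10% |
|---|---|---|---|
| 80 / 80 | 77.7 | 77.7 | 0.0001 |
| 80 / 75 | 25.9 | 25.9 | <0.0001 |
| 70 / 70 | 66.8 | 66.8 | 0.0007 |
| 70 / 65 | 21.7 | 21.7 | <0.0001 |
| 60 / 60 | 61.2 | 61.2 | 0.0014 |
| 60 / 55 | 19.9 | 19.95 | <0.0001 |

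All entries are percentages. A simulation of the unstratified Miettinen-Nurminen test (400,000 runs per row) at -10% gives 78.0, 25.9, 66.8, 21.5, 61.3 and 19.4%, which is close throughout.

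**Step 4: what it would take to pass the +10% rule (control 70%)**

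| True Substudy B rate | Advantage | Probability of passing +10% |
|---|---|---|
| 80% | 10 points | 2.5% |
| 85% | 15 points | 26.4% |
| 90% | 20 points | 80.5% |

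**Step 5: the observed difference needed (control 80%, simple unpooled interval)**

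- +10% rule: about +15.7 points. With 95.7% observed, SE = √[(0.16 + 0.957 × 0.043) / 240] = 0.02895, and 0.157 - 1.96 × 0.02895 = 0.1003.
- -10% rule: about -2.7 points. With 77.35% observed, SE = √[(0.16 + 0.7735 × 0.2265) / 240] = 0.03737, and -0.0265 - 1.96 × 0.03737 = -0.0997.

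**Step 6: the GMR rule**

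Table 11 reproduces with the 0.67 threshold and a log-scale SD of 1.35: 90.1, 66.8 and 30.1% against the stated 90.0, 66.6 and 30.0%. The inconsistency is confined to seroresponse.

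**The case against.** The strongest reply is that nobody could be misled. The formal hypotheses and the SAP give -10%, and the power table fits only -10%. Section 10.8.9.3 describes itself as a summary, and Section 9 leaves the detail to the SAP. A +10% bound cannot be what the word noninferiority means. The SAP lists no departures from the protocol's plan (Section 2.1), which suggests its authors read the protocol rule as -10%. Section 2.2.1 also reports higher seroresponse in the vaccine-naïve group, the direction in which a -10% rule is most easily met. On this view it is an erratum with no practical effect.

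Most of that stands. The intended rule is recoverable, and nothing in the documents suggests that +10% was ever applied. The near-zero power describes the table's wording, not what the sponsor is likely to have done. What does not follow is that the text can stay: this is the success criterion of a primary hypothesis, in the section that defines its analysis.

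A second reply is that the minus sign may have been lost in converting the PDF to text, since other hyphens in the document are irregular. That cannot be excluded without looking at the approved PDF. The sign is intact in Section 10.8.9.1 and in SAP Section 5.1.1, though, so there is no positive reason to think so.

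**Conclusion.** The concern holds. Protocol Section 10.8.9.3.2 contradicts Section 10.8.9.1, SAP Section 5.1.1 and Table 12 on the threshold for the second primary hypothesis of Substudy B. The two rules differ by 20 percentage points. At equal rates of 80% the chance of success is 77.7% under one and about 0.0001% under the other; across all of Table 12 the +10% rule succeeds at most about 0.001% of the time.

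The power figures assume 240 evaluable per group, 1-sided alpha 0.025, an unstratified analysis and a normal approximation, and they concern the seroresponse test alone, not the sequence with the GMR. The contradiction itself needs none of these assumptions. It is a wording error in a decision rule, not a flaw in the design, sample size or SAP. It still has to be corrected, because a confirmatory criterion should have one value.

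**What to change.** In the Immunogenicity row of the table in protocol Section 10.8.9.3.2, change the seroresponse threshold to greater than -10%, after checking the approved PDF to confirm that the sign is missing there. Section 10.8.9.1, SAP Section 5.1.1 and Table 12 need no change.

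Ask the sponsor to confirm that the Substudy B noninferiority conclusion reported in Section 2.2.1 was reached with the -10% rule. The documents do not say, so this is a query and not a finding.

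The cost is one character in the next amendment or an administrative correction, with no effect on data, sample size or analysis.
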